Across the sites 60 patients will be enrolled to achieve 40 FEAST patients who will fully complete this study at the MUSC Institute of Psychiatry, Brain Stimulation Service (BSS) in Charleston, SC, and at GRU in Augusta, GA and Aiken, SC. At both MUSC and GRU, roughly matched 30 patients (each) will also be recruited from those scheduled to receive UB RUL ECT to obtain a cohort of 40 RUL comparison patients. The FEAST and UB RUL ECT groups must meet identical inclusion/exclusion criteria and will undergo identical evaluation procedures. The only difference between the groups will be that one receives FEAST and other UB RUL ECT. The treatment received by the UB RUL ECT group will not be affected by participating in this protocol. This is an open label, non-randomized, non-masked study. Separate consent forms will be used in each group. We are thus asking FDA permission to study 60 patients with FEAST. An additional 60 patients will be studied who receive conventional ECT. Even though they are getting conventional ECT, they are covered by this FDA IDE as their data will be used for comparison purposes with FEAST.

Patients will be selected from those referred for ECT for the treatment of major depressive episode. To verify diagnosis, the SCID-P will be administered to derive DSM-V diagnosis (unipolar or bipolar major depressive episode) and relevant subtypes and specifiers (American Psychiatric Association, 2013).

Inclusion and exclusion criteria are presented in Table 2. Briefly, patients will be between the ages of 18 and 90 years and will provide informed consent. Exclusions include: history of schizophrenia, schizoaffective disorder or any non-mood disorder psychosis, rapid cycling bipolar disorder, central nervous system illness other than conditions associated with psychotropic exposure, alcohol or substance abuse or dependence in the past 3 months, pregnancy, epilepsy, inability to have stable medications, and ECT within the past six months.

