The measures of Clinical Status and Characteristics in Table 3 are essentially unchanged since the original IDE. The cognitive battery is considerably reduced. This was done since the primary goal of this study is the comparison of the groups in EEG manifestations of seizure, with comparisons of efficacy and side effects secondary. Second, none of the dropped measures showed significant change with FEAST administration in our prior analyses, and the literature on traditional ECT has only shown persistent deficits for retrograde memory for autobiographical events ([name], 2014b). The measures that were retained serve a particular purpose: (1) the mMMS at baseline is used for sample characterization and matching of the two groups. A significant difference between the groups would denote an effect pertaining to global cognitive status. This is not expected. (2) Orientation recovery will be assessed at each treatment (but obviously not at preFEAST baseline). This measure has been extremely sensitive to differences in ECT treatment modalities (sine wave vs. brief pulse; ultrabrief vs. brief pulse, BL ECT vs. RUL ECT, etc.) and has been found to predict long-term deficits in autobiographical memory (Sabin et al., 1995b). We expect the FEAST group to manifest faster recovery of orientation than the UB RUL ECT group, even though the latter has manifested remarkably rapid recovery compared to other ECT modalities ([name] et al., 2008). (3) The most critical measure is the CUAMI-SF. This measure has repeatedly shown differences between modalities and has the strongest evidence for persistent deficit following ECT. While effects of UB RUL ECT on this measure have been slight (compared to retested normal controls), nonetheless we predict an advantage for FEAST in this measure of autobiographical amnesia. (4) The Attitudes Interview collects patient self-report on the effects of the treatment course on mood

and memory. A global assessment is given by the patient, akin to a clinical global impression (CGI) for each domain. Recent research has shown that these are the only self-report measures in the history of ECT research to show significant covariation with objective cognitive deficits and with type of ECT modality (Berman et al., 2008, Brakemeier et al., 2011b). We predict that the FEAST and UB RUL ECT groups will be equivalent in self-report of effects on mood, but the FEAST group will report less deleterious impact on memory.

B. 5a MRI scan

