There is no stipulated minimum or maximum treatments for patients to be classified as provisional responders; the aims are to achieve maximal improvement in each patient without exposing them to unnecessary treatment. In patients who have shown substantial benefit (>40% improvement in HRSD₂₄ score), treatment is continued until there is a plateau over at least two treatments (i.e., change in

HRSD₂₄< 3 points) or it is judged that maximal improvement has been achieved (ie, HRSD₂₄≤ 5). In patients who have shown more than 40% improvement, a minimum of 10 treatments will be required before classification as a nonresponder. In patients with <40 % improvement, treatment may be stopped when a plateau in improvement has obtained and the patient has received at least 6 treatments. After 5 treatments, there is the option of increasing electrical dose from 6xST to 9xST. Thus, the trajectory of symptomatic change is closely monitored. These criterion ensure an adequate trial of ECT ([name], 1986b) before declaring nonresponse, while not exposing patients who respond rapidly or patients who show no benefit to excessive treatment.

Non-responders to FEAST will be offered a course of traditional ECT, first using high dosage RUL with a standard pulse width (i.e., 0.5-1.0 ms), and, if necessary, switching to bilateral ECT. The efficacy evaluation procedures will be repeated after this second (Mode 2) course.

Participation in this protocol terminates following the acute completion of the final assessments (clinical, neuropsychological, and fMRI). Patients will be followed up at 2,4, and 6 months. At that 6 month visit they are fully terminated from the study. Of note, after the acute phase is over, FEAST patients resume fully standard care at the discretion of the ECT team and the referring physicians. We will document medication changes and whether they require additional ECT during the 6 month followup.

B.7 Ultrabrief RUL ECT Treatment Procedures

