FEAST and ultrabrief RUL ECT patients will be treated identically except as noted below. The traditional d'Elia electrode placement will be used for UB RUL ECT (American Psychiatric Association, 2001), with the frontotemporal electrode tangential to the midpoint of the line connecting the right auditory tragus and the canthus. The posterior electrode will be tangential to the vertex (midpoint of line connecting nasion and inion). Standard stainless steel 2" diameter electrodes will be used. If it is deemed that patients require a change in ECT modality, a switch to either brief pulse RUL or BL ECT will be implememnted, as clinically indicated.

B.8 Assessment of Efficacy

Clinician ratings. Instruments include the HRSD (24-item) (Hamilton, 1967), MADRS (Montgomery and Asberg, 1979), CGI (severity and improvement) (Guy, 1976), and the GAS (Endicott and Spitzer, 1978). A clinical evaluation team independently completes these scales on the basis of conjoint interviews, both at set time points (preECT baseline, 1-2 days after ECT termination) and the HRSD alone is also completed at spaced intervals (weekly during the ECT course). Interviews usually take place between 10 AM-12 PM to minimize variability due to diurnal variation.

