Oreintation recovery time will be assessed at every treatment session. The most profound cognitive effects of ECT are expressed in the postictal period (Daniel and Crovitz, 1983a, Daniel and Crovitz, 1983b, [name], 1986a). The repeated assessment (every treatment) strongly enhances reliability of measurement, and allows for examination of progressive change over the treatment course (Calev et al., 1991a, Calev et al., 1991b, [name] et al., 1986). The measurement of orientation recovery has been particularly sensitive to variation in ECT electrode placement, waveform, and dosage. Further, it has been repeatedly found to be a potent predictor of the degree of retrograde amnesia following the ECT course, even in the long-term (Sobin et al., 1995b). Following seizure termination, orientation (5 items) is assessed continuously until the criterion for full recovery is met or 90 min elapse. The critierion for recovery is correct response to 4 of the 5 items. The 5 questions pertain to name, birth date, age, place, and day of the week.

The mMMS, Buschke Selective Reminding Test (BSRT) and CUAMI-SF will be administered at baseline and at follow-up (during the week following FEAST or UB RUL ECT). The modified form of the MMS provides a total socre of 57 (as opposed to 30 with the original version) and broader coverage of gross cognitive abilities (Mayeux et al., 1981, Stern et al., 1987). The primary use of the mMMS is sample characterization, especially since there is evidence that low baseline scores predict more severe short- and long-term retrograde amnesia (i.e., cognitively-compromised paitents are more vulnerable to the key adverse effect on memory) (Sobin et al., 1995a). No change is expected in mMMS scores in either group. However, as a safety measure, the two groups will be compared in change in mMMS scores to verify this assumption and assure that there was no change in global congitive status.

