The primary analysis for Hypothesis 4 will use all available HRSD₂₄ data (i.e., the intent-to-treat data) from the FEAST and UB RUL ECT samples. A random regression model will be used to examine the relationship between HRSD₂₄ scores and treatment group. Time will be the within-subjects repeated measures factor, site and treatment group the between-subjects factors, with medication-resistance classification and baseline HRSD₂₄ serving as covariates. All interactions with time will be modeled. In secondary analyses, we will also include age, gender, age-at-onset of illness, and duration of current episode as covariates, if pre-screening indicates utility. We will investigate whether HRSD₂₄ scores are linear in time or quadratic, cubic, or piece-wise linear (e.g., hockey-stick shaped). Indeed, in a study comparing several different statistical methods in their sensitivity to ECT treatment groups differences in rate of clinical improvement, we found that the HRSD₂₄ scores over time were frequently nonlinear (Nobler et al., 1997a). The type of analysis conducted on HRSD₂₄ scores will be repeated for secondary analyses with the MADRS, IDS-SR, and CGI-S.

FEAST and UB RUL ECT will also be compared in the categorical outcomes of final remission status (HRSD₂₄ of 10 or less at post-treatment) in a secondary analysis to gauge generality of the effect and clinical significance. Nominal logistic regression analysis will be used to compare the treatment groups in covariate-adjusted odds of remission. Remission status will be the dependent variable. The independent variables will be the treatment group indicator, along with site, medication resistance, and baseline HRSD₂₄.

Hypothesis 5. In two primary cognitive measures, orientation recovery time and CUAMI-SF scores, FEAST will have a significant advantage relative to UB RUL ECT.

The cognitive measures were described in Section B.12. Orientation time will be averaged within each patient across all treatments. An ANCOVA will be conducted on these values with Site and Treatment Group as between-subject factors, and age and number of treatments in the average as covariates. A similar ANOVA will be conducted on CUAMI-

SF scores, with Site and Treatment Group as between-subject factors, and age, number of treatments, and baseline CUAMI-SF score as the covariates.

Hypothesis 6. FEAST will have a significant advantage in the subjective global evaluation of the effects of ECT on memory.

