We do not anticipate that this form of ECT (unidirectional, ultrabrief pulse with spatial targeting) will have an adverse impact on efficacy, although this is not certain. Potential lack of efficacy likely constitutes the most significant risk of FEAST. Precautions have been taken in this protocol to mitigate this risk. First, patients who do show sufficient benefit after 5 treatments may receive a dosage increment, increasing the stimulus dose from 6xST to 9xST. In the community, dosing of UB RUL ST is often 8xST or more (e.g., (Loo et al., 2012)). Second, any patient who completes the research phase as a nonremitter will be offered a course of traditional ECT (UB RUL ECT, high dose RUL or BL ECT). Our preliminary experience in 35 patients clearly indicates that FEAST has potent antidepressant properties. We cannot, however, say with assurance that these properties are equivalent to traditional forms of ECT, without explicit comparison. This study provides important data in this respect, involving the first cotemporaneous comparison of FEAST and UB RUL ECT, albeit in a non-randomized and non-masked fashion. It is anticipated that the findings obtained here will provide the foundation for a subsequent RCT.

The protocol involves monitoring of objective and subjective side effects and includes provision for alternative treatment for patients who do not respond clinically. Although a large number of procedures are conducted, other than ECT, they are all noninvasive. Patients who consent to the protocol have the option of declining participation in specific procedures (e.g., fMRI studies), but can retain participation in the remaining procedures.

Finally, FEAST might present with two theoretical risks: superficial skin burn and intracerebral damage to excessive current density). The use of an electrode with small surface area could increase the impedance in the circuit and result potentially in skin burn or prevent the passage of the stimulus. This theoretical risk is minimized by the fact that the ECT device voltage limits and immediately aborts stimulus delivery when excessive impedance is encountered. In this protocol, we are requesting that the voltage/impedance

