1. FEAST uses a form of RUL ECT. Given the fact that it is more focal than traditional RUL ECT, with sparing of right medial temporal lobe areas expected, the electrode position should have advantages relative to both BL and traditional RUL ECT.
2. FEAST not only uses the 0.3 ms pulse width (ultrabrief) found to result in marked cognitive savings, but also uses a unidirectional waveform that is expected to confer additional advantages due to greater efficiency.
3. Stimulus dosage in this protocol is adjusted relative to the seizure threshold determined for each patient. The dosage relative to seizure threshold was selected based on evidence that this is the dose at which traditional RUL exerts maximal efficacy. A further dosage increment (9xST) is permitted only in the context of insufficient improvement.
4. FEAST will be administered at a schedule of three treatments per week. If patients show clinical benefit, but side effects are severe, the study physician may order that treatment frequency be reduced to twice per week.
5. The number of treatments administered is regulated. Treatment is continued until there is a plateau in improvement over two treatments. For patients with substantial clinical improvement (\geq 40% change in HRSD₂₄ scores) a minimum of 10 treatments is required before declaring nonresponse. In patients with more modest improvement (< 40% change in HRSD₂₄ scores) the minimum is reduced to 6 treatments. Patients who manifest remission or plateau after substantial improvement can exit treatment at any time. Thus, the number of treatments is titrated to the clinical progress of patients and lack of further improvement over two treatments results in termination of the treatment course. These methods minimize the number of treatments administered

while simultaneously allowing each patient ample opportunity to attain remission. The same guidance will apply to the cotemporaneous UB RUL ECT sample.

6. Anesthetic dosage is adjusted for each patient. At the first treatment, the dose of methohexitol is set at 1.0 mg/kg. Based on anesthetic response, this dose is then adjusted for the subsequent treatments.

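### Hypothesis 5 averages orientation time over all sessions, so sessions given after an ultrabrief RUL patient switches modality during the course would count in the comparator mean

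*Combined protocol and SAP*

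**What the plan says.** Section IV.B.15, Hypothesis 5, names orientation recovery time as one of two primary cognitive measures. The rule for it is: "Orientation time will be averaged within each patient across all treatments". The ANCOVA has site and treatment group as factors, with age and the number of treatments averaged as covariates. It has no term for the modality actually given. Section IV.B.12 sets the measurement schedule: "Oreintation recovery time will be assessed at every treatment session". Sessions after a switch would therefore be measured too.

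For the comparator, Section IV.B.7 provides: "If it is deemed that patients require a change in ECT modality, a switch to either brief pulse RUL or BL ECT will be" made where clinically indicated. It gives no timing and does not say what happens to the data. Section IV.B.1 adds: "The treatment received by the UB RUL ECT group will not be affected by participating in this protocol". Section IV.B.6 (RUL ECT Stimulus Dosing) leaves comparator care to routine practice, and the end of Section IV.C.5 describes these patients as due to start on UB RUL. The dropout rules in Section IV.B.9 do not list a modality switch.

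Two places limit the exposure. Section IV.C.3, item 5, ends a course when improvement stalls over two treatments, and says: "The same guidance will apply to the cotemporaneous UB RUL ECT sample". Section IV.C.4 places the post-course evaluations of both groups before any alternative acute treatment. For FEAST, Section IV.C.2 says that "any patient who completes the research phase as a nonremitter will be offered a course of traditional ECT", and Section IV.B.6 treats this as a second course: "The efficacy evaluation procedures will be repeated after this second (Mode 2) course".

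**The concern.** Section IV.B.5 says of orientation recovery: "This measure has been extremely sensitive to differences in ECT treatment modalities". Its examples include ultrabrief against brief pulse and bilateral against RUL, the two changes that Section IV.B.7 permits. Section III.C.5 links wider pulse width and bilateral placement to more intense cognitive effects. Read literally, the rule lets slower-recovery sessions into the UB RUL mean, so the contrast becomes FEAST against a mixture.

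The gap falls mainly on one side, because conventional ECT for FEAST patients comes in a separate later course. The expected push is in the direction that Hypothesis 5 predicts. Section IV.B.15 wants clearly specified outcome measures to protect the Type I error, and intends the effect sizes to power a later randomized trial. In an open-label study, leaving the eligible sessions undefined also allows that choice to be made after the data are seen.

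**Working it through.** The plan gives no power, effect size or alpha for Hypothesis 5, so there is no figure to reproduce. I first settle who is exposed, then illustrate the size.

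**1. Who can contribute post-switch sessions**
- UB RUL patients who plateau: the course ends (IV.C.3, item 5) and alternative treatment follows the post-course evaluations (IV.C.4). Little exposure.
- UB RUL patients switched before the course ends: allowed by IV.B.7, and their sessions count under the literal rule. Exposed.
- FEAST patients given conventional ECT: a separate course after the research phase (IV.B.6, IV.C.2). Naturally outside the average.

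**2. Inputs from the documents**
- 40 completers per group (IV.B.1).
- Sessions per patient: mean 8.8, range 4 to 14 (III.D.6).
- SD of orientation time in the FEAST pilot: 6.4 min (Section I), 7.5 or 9.6 min (III.D.6). These use different starting points for the clock.
- Within-patient session SD: 6.5 min, from the UB RUL sessions of one patient (III.D.6).
- The only between-modality gap in minutes: 21.6 − 14.7 = 6.9, for UB RUL against FEAST in that same patient. This is not the contrast needed and serves only as a stand-in.

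**3. Assumptions, not in the documents**
- Two-sided 5%, hence 2.5% in FEAST's favour.
- 10% or 20% of UB RUL patients switch, after 6 sessions (the minimum in IV.B.6 before stopping for limited improvement), followed by 6 more sessions.
- Post-switch sessions run 6.9 or 10 min longer.
- An equal share of FEAST patients stops at 6 sessions.

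**4. Raw shift in the UB RUL mean** = share switched × share of sessions after the switch × extra minutes
- 0.10 × 0.5 × 6.9 = 0.35 min
- 0.20 × 0.5 × 6.9 = 0.69 min
- 0.20 × 0.5 × 10 = 1.0 min

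**5. Planned ANCOVA, no true difference** (10,000 simulated trials per case; site, group, their interaction, age and treatment count). The count covariate absorbs part of the shift, because switchers have longer courses.

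| Switched, extra min | ANCOVA bias | False FEAST advantage, SD 7.5 | SD 6.4 | SD 9.6 |
|---|---|---|---|---|
| 10%, +6.9 | 0.30 min | 3.5% | 3.8% | 3.1% |
| 20%, +6.9 | 0.52 min | 4.6% | 5.1% | 4.1% |
| 20%, +10 | 0.76 min | 5.9% | 6.8% | 5.0% |

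A hand check at SD 7.5 uses SE = 7.5 × √(2/40) = 1.68 and rate = Φ(bias/SE − 1.96). The three rows give 3.7%, 4.9% and 6.6%. This check leaves out session-level noise and the spread that switching adds, so slightly higher values are expected.

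Varying the share of FEAST patients who stop at 6 sessions from 53% to 0% moves the 20% cases to 0.36–0.61 min (+6.9) and 0.52–0.88 min (+10), with rates of 3.8 to 7.0% at SD 7.5.

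**6. Scale.** The difference detectable with 80% power is 2.80 × SD × √(2/40): 4.0 min at SD 6.4 and 4.7 min at SD 7.5. The illustrated biases are well below that.

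**7. Entry-modality sessions only.** The ANCOVA bias is 0.01 min and the rate 2.4%.

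**The case against.** The strongest case is that Section IV.B.7 never says a switch happens during the course. Its targets resemble the FEAST second course, Section IV.C.5 uses the word switch for that FEAST step, and Section IV.B.7 opens by saying that the groups are treated alike apart from noted exceptions. With the plateau rule and Section IV.C.4, most UB RUL non-responders would finish the course and be assessed before receiving anything else. This largely stands, and it confines the point to patients switched earlier. It does not remove the point: the switch sentence is itself one of the noted exceptions, routine care governs this group, and no text excludes post-switch sessions.

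It is also fair that averaging every session of a treatment strategy is a legitimate target. But Section IV.B.15 attaches intent-to-treat to the efficacy analyses, and Hypothesis 5 asks about FEAST against UB RUL. A strategy average would also have to count FEAST second-course sessions, which the plan does not propose.

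Finally, the sizes rest on assumptions and are small beside the limits of a non-randomized, unmasked comparison that Section IV.B.5 calls secondary to the EEG aim. That stands too.

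**Conclusion.** The gap is real but conditional, and probably small. It concerns only UB RUL patients who change modality before their course ends, and for them the likely direction favours FEAST. Its size is unknown. The 0.3 to 0.8 min and roughly 3.5 to 6% depend on the assumed switch rates, the 6 + 6 session split and a time gap borrowed from one patient and a different contrast.

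A reader might infer more, in three ways that the documents do not support:
- **That UB RUL non-responders generally feed the average.** The response rates in Section III.B.1 leave 10–20% to 40–50% non-responders, but that is a pool, not a switch rate, and most of that pool would leave the course first.
- **That the false-positive rate could become very large.** A simple two-sided calculation reaches 79.8% at SD 6.4, but only with 40% switched and 20 extra minutes per post-switch session. Neither figure comes from the documents, and the calculation ignores the covariates.
- **That the direction is open because FEAST second-course sessions might count.** Counting them could reverse the sign, but the protocol makes that a separate course and repeats only efficacy evaluations after it.

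This is a worthwhile, inexpensive improvement to a primary cognitive measure, not a flaw that undermines the study.

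**What to change.** Add one or two sentences to Hypothesis 5. In both groups, compute the primary orientation mean, and the treatment-count covariate that goes with it, from entry-modality sessions only: FEAST sessions in the FEAST group and UB RUL sessions in the comparator. Report the all-session mean as a sensitivity analysis, with the number of switches by group. Apply the same restriction to the EEG averages across treatments in Section IV.B.13.

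No new data are needed and care does not change. The cost is that switchers contribute fewer and earlier sessions. With 6 instead of 12, the session-noise standard error of a switcher's mean rises from 6.5/√12 = 1.9 to 6.5/√6 = 2.7 min. Section III.C.5 says that recovery speeds up over an ultrabrief RUL course, so early sessions run longer. With an assumed gain of 0.5 min per session and 20% switched, the mean session number is (8.8 + 1)/2 = 4.9 for a typical course and (6 + 1)/2 = 3.5 for a switcher. The raw UB RUL mean then rises by about (4.9 − 3.5) × 0.5 × 0.20 = 0.14 min. The planned count covariate removes this if the trend is linear and the same in both groups.
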